We will compare the TES to an eTreatment As Usual (eTAU) consisting of current care plus access to a website [<http://compass-care.northwestern.edu/>] that will provide content specific to perinatal depression.

We will utilize a randomized clinical trial (RCT) to compare a technology enabled service (TES) intervention to enhanced treatment as usual (eTAU) within antenatal and postpartum women. Randomization will occur at the patient level. It is not feasible to mask participants or providers.

The primary effectiveness outcome is depression severity. Secondary outcomes are anxiety, and satisfaction with care.

Aims

Aim 1: Conduct a pilot Optimization-Effectiveness-Implementation (OEI) hybrid trial of a Technology Enabled Service (TES) for the treatment of depression compared to enhanced treatment as usual (eTAU).

Aim 2: Experimental therapeutics aims. Analyses will explore the mediating effects of the CM dashboard features that support the CM's treatment activities and workflow, including tracking symptom response, managing the stepped care processes, and communicating care plans. We will also explore the moderating effects of race, ethnicity, income, age, anxiety symptom severity, and mobile phone competence on the depression outcome.

BACKGROUND

Note: The "Background" section has been significantly reduced to create a more succinct protocol document. The original grant submission with the full background information is available upon request.

1. Perinatal depression is common and associated with adverse maternal and child outcomes.¹⁻⁵

Glossary of Terms:

- a. **Perinatal:** relating to the time, usually a number of weeks, immediately before and after birth.
 - a. **Antenatal:** before birth; prenatal.
 - b. **Postpartum:** The period just after delivery, as with postpartum depression. Postpartum refers to the mother, and postnatal to the baby.

2. Myriad barriers to effective treatment exist.⁶⁻¹¹

3. Collaborative Care (CC) represents an innovative health systems approach to depression treatment.¹²⁻²⁰

4. Perinatal Depression poses unique care challenges.²¹⁻²²

5. Significant gaps exist in Perinatal CC implementation.²³⁻²⁶

6. Technology enabled services (TES) may offer a solution for effective Perinatal CC delivery.

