TESs can (a) include dashboards/interfaces to automate Care Manager (CM) tasks and streamline CM workflows for population-based case review; (b) connect the CM to both patients and providers, facilitating communication about stepped care among the entire care team; and (c) directly deliver digital treatments to people who are unable to engage in person due to logistical barriers common in the Perinatal period. Smartphones are broadly available among reproductive aged people and are owned by 94% of Americans under age 30 and 89% ages 31-49.²⁷⁻²⁹ Several RCTs have shown that digital interventions delivered through smartphones are effective in reducing Postpartum Depression.³⁰ As such, a TES can integrate a seamless service in which adherence to the core tenets of CC are facilitated by

STU#:00211815

digital technologies, but this novel application of TES has not been previously studied.

STUDY ENDPOINTS

We will utilize a pragmatic, RCT based on our OEI hybrid trial design.⁵³⁻⁵⁵ A total of 85 people (75 from Northwestern and 10 from Women and Infants Hospital) will be randomized to either TES or enhanced treatment as usual (eTAU). Descriptions of the TES and eTAU interventions appear in the next section labeled “Study Intervention(s)/ Investigational Agent(s).” Depressive symptoms and other outcomes will be measured at baseline and at 6 and 12 weeks. Beyond 12 weeks, participants will be allowed to continue use of the TES app and the eTAU website for the duration of the grant-funded budget period. App and website use will be tracked for the entire study duration.

STUDY INTERVENTION(S) / INVESTIGATIONAL AGENT(S)

Participants will be assigned to receive one of two study interventions: (1) a Technology Enabled Service, or (2) Enhanced Treatment as Usual. The design of the TES and eTAU interventions were determined through the design study (STU# STU00211314) and negotiations with our software development contractor (Adaptive Health).

Technology-Enabled Service (TES)

The TES will be based on Adaptive Health’s IntelliCare platform (described below). The TES will permit use of text message communication. Text message content will meet HIPAA standards, and will not contain information that might identify the patient as being in treatment for depression. Text message communication may be used to encourage IntelliCare app use or arrange phone calls to avoid risk of loss of confidentiality.

IntelliCare

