Effectiveness analyses will use intention to treat methods. To compare overall effectiveness, generalized linear mixed models (GLMM) will be used to determine if there are differences in effectiveness between individuals receiving TES and eTAU over time. Missing data will be examined for potential non-ignorable mechanisms, and will be managed through multiple imputation. Additional covariates will also be included to identify any substantive changes in the service, technologies, and/or implementation plan as a result of optimization. We will examine moderation of treatment arm by strata (postpartum or antenatal), and present results within each strata.

Moderation of TES on effectiveness. We will examine any moderation of the effect of treatment arm on depressive symptoms by race, ethnicity, age, health status, substance/alcohol use, mobile phone competence, or other mental health treatments, in individual GLM models, by estimating a treatment by moderator interaction in predicting end of treatment depression scores adjusting for baseline levels of depression.

Power. Although a pilot study, we provide an estimate of effect that we can detect with 100 randomized participants, as well as within strata of 80 and 20. As power calculations for repeated measures involve correlations over time which are speculative at this point, we provide effect size estimates for 12 month PHQ-9 scores based on an independent t-test. We have 80% power to detect an effect size of 0.58 for the entire cohort – a difference in PHQ-9 scores between eTAU and TES of 2.9 assuming a SD of 5; and effect sizes of 1.41 and 0.65 in antenatal and postpartum populations, which correspond to differences of 7.03 and 3.26 on the PHQ-9).

PROVISIONS TO MONITOR THE DATA TO ENSURE THE SAFETY OF PARTICIPANTS

Data and safety monitoring of participants will be monitored by the Principal Investigator, [name], who have primary responsibility for monitoring and will do so on a weekly basis during their planned meetings. [name] will regularly review all data and adverse events and will report all serious adverse events to the Northwestern University Institutional Review Board Requirements. Second, any reporting of significant mental or physical health-related symptoms by the participant to the study team will result in appropriate referrals to the participant's clinician or other appropriate facilities.

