Evaluating Technology Enabled Services in Perinatal Depression

NCT05525689

04.15.24

Data Analysis Plan

Effectiveness. Effectiveness analyses will use intention to treat methods. Given potential bias due to the time delay of implementation, a comparison of population characteristics (race and ethnicity, age, gender, health status, mobile phone competence, baseline depression and other mental health treatments) must be made between patients receiving TES and the eTAU. Should the populations be different, propensity scores will be estimated for the likelihood of receiving TES, and models will adjust for those scores (trimming the data as necessary). After the population comparison and appropriate adjustment, we will compare overall effectiveness, using generalized linear mixed models (GLMM) to determine if there are differences in effectiveness between individuals receiving TES and eTAU over time, while accounting for intraclass correlations (ICC) within CMs, and clinics where necessary. Missing data will be managed through multiple imputation. Additional covariates will also be included to identify any substantive changes in the service, technologies, and/or implementation plan as a result of optimization.

Moderation of TES on effectiveness. We will examine any moderation of the effect of treatment arm on depressive symptoms by race, ethnicity, age, health status, substance/alcohol use, mobile phone competence, or other mental health treatments, in individual GLM models, by estimating a treatment by moderator interaction in predicting end of treatment depression scores adjusting for baseline levels of depression.

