Power. Although a pilot study, we provide an estimate of effect that we can detect with a conservative recruitment of 30 participants in eTAU and 45 participants in TES. As power calculations for delayed roll-out trials involve both between period and within period autocorrelations, which would be speculative at this point, we estimated an effect size with an estimated ICC of 0.01 within clinics. With this assumption, we have 80% power to detect an effect size of 0.76 – a difference in PHQ-9 scores between eTAU and TES of 3.8 assuming a SD of 5. Given this trial is embedded in the COMPASS CC program that receives 30-50 referrals per month, we expect this trial will be able to enroll more participants than this conservative estimate, and as this is the calculated effect size for a simpler analysis, we anticipate this to be conservative estimate.

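### The primary model does not commit to adjusting for baseline PHQ-9, and the SAP brings baseline depression in only if the arms look different; always adjusting would usually be more precise at almost no cost

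*Protocol*

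**What the plan says.** **Primary model.** In the Protocol (Data Analysis Plan), "generalized linear mixed models (GLMM) will be used to determine if there are differences in effectiveness between individuals receiving TES and eTAU over time". The only covariates named are those that mark changes made during optimization. The SAP (Effectiveness) repeats the model and adds correlation terms, "while accounting for intraclass correlations (ICC) within CMs, and clinics where necessary".

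**Baseline depression in that model.** The SAP lists seven characteristics to compare between arms, baseline depression among them. It gives the reason as "Given potential bias due to the time delay of implementation, a comparison of population characteristics". Adjustment is conditional: "Should the populations be different, propensity scores will be estimated". No criterion for a difference is given. The Protocol has no such step.

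**Baseline depression elsewhere.** The moderation models in both documents estimate an interaction "in predicting end of treatment depression scores adjusting for baseline levels of depression", with no condition attached.

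**Design.** The Protocol (Study Endpoints) says "Depressive symptoms and other outcomes will be measured at baseline and at 6 and 12 weeks". Under Objectives it says "Randomization will occur at the patient level". The SAP (Power) instead reasons from a staggered design: "As power calculations for delayed roll-out trials involve both between period and within period autocorrelations".

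**The concern.** A model of PHQ-9 over time can treat the week-0 score in four ways, and the documents do not say which applies:

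1. leave it out and analyse follow-up only;
2. make it a response with a free mean in each arm, so that the treatment effect is a difference in change;
3. make it a response with one mean common to both arms;
4. use it as a covariate.

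Options 3 and 4 use the baseline fully. Options 1 and 2 usually give a wider interval. The documents also do not say which contrast is the treatment effect.

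The one explicit rule, in the SAP, makes adjustment depend on the observed baseline comparison. It also enters baseline depression only as part of a score shared with six other characteristics. The precision of the main comparison therefore rests on an unstated choice and a data-dependent trigger. In a pilot planned around 75 to 100 people, a baseline score already in hand is the cheapest way to narrow the interval.

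**Working it through.** **Inputs from the documents.** SD 5 and 80% power (both Power sections); 85 planned (Protocol, Study Endpoints); 30 eTAU and 45 TES (SAP, Power).

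**Assumed.** Two-sided 0.05; 85 split 43/42; no dropout; no clustering; equal SDs at week 0 and week 12 unless stated. The baseline to week-12 correlation r is not in the documents, so results are given for r = 0.3/0.5/0.7.

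**The plan's own figures.**
- *Protocol.* An independent t-test with 50 per arm gives an effect size of 0.566 (2.83 points). Power at the stated 0.58 is 0.819, so the figure is reproduced closely. An exact 0.58 needs 47 to 48 per arm or a 60/40 split.
- *SAP.* 30/45 without clustering gives 0.669 (3.35 points). The stated 0.76 implies a design effect of (0.76/0.669)² = 1.29.

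Neither calculation contains a baseline term, and neither is wrong because of this point.

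**Detectable difference.** This is δ × 5 × √[f(1/n₁ + 1/n₂)]. Here δ is the noncentrality giving 80% power (about 2.83 at 43/42 and 2.84 at 30/45), and f is the relative variance:
- follow-up only: f = 1, df N−2;
- change score: f = 2(1−r) = 1.4/1.0/0.6, df N−2;
- baseline-adjusted: f = (1−r²)(1 + 1/(N−4)), df N−3. The second factor is the price of estimating the slope. At N = 85, f = 0.921/0.759/0.516.

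Example, 43/42 follow-up only: 5 × √(1/43 + 1/42) = 1.085, and 1.085 × 2.835 = 3.07.

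| Analysis | 43/42, r = 0.3/0.5/0.7 | 30/45, r = 0.3/0.5/0.7 |
|---|---|---|
| Follow-up only | 3.07 throughout | 3.35 throughout |
| Change score | 3.64/3.07/2.38 | 3.96/3.35/2.59 |
| Baseline-adjusted | 2.95/2.68/2.21 | 3.21/2.92/2.41 |

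Without the slope and df cost, the adjusted figures would be 2.93/2.66/2.20 and 3.19/2.90/2.39. The cost is therefore about 0.01 to 0.02 points. Adjustment breaks even with follow-up only at r = 0.11 (43/42) or 0.12 (30/45).

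**Baseline as a response.** Three visits with equal correlations, 50 per arm, r = 0.5, SE of the week-12 contrast: free arm means 1.00; common baseline mean 0.866; covariate adjustment 0.866.

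**Smaller baseline SD.** Entry cut-offs on PHQ-9 and GAD-7 make this plausible. With baseline SD 4 (assumed), the change-score factor is 1 + 0.8² − 2(0.8)r, giving 3.31/2.82/2.22 at 43/42. The gain from adjustment over change scores shrinks from about 0.7/0.4/0.2 to 0.36/0.14/0.01.

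**The conditional route.** The SAP gives no trigger, so one was assumed: any of seven independent characteristics differing at p < 0.05. That fires in 1 − 0.95⁷ = 30% of trials. The simulation used 60,000 trials per r, with only baseline PHQ-9 prognostic, the score entered as a covariate, and no trimming. Variance at 43/42 relative to an unadjusted follow-up comparison:

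| Rule | r = 0.3/0.5/0.7 |
|---|---|
| Follow-up only, triggered propensity score | 0.99/0.92/0.79 |
| PHQ-9 always | 0.91/0.76/0.52 |
| PHQ-9 always, plus triggered score | 0.95/0.79/0.54 |

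A separate check put the same triggered score on change scores. It gave 1.20/0.90/0.59, against 0.96/0.77/0.55 for baseline adjustment plus the trigger.

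**The case against.** The strongest reply is that the model is unspecified, not shown to ignore baseline. A single-endpoint moderation model has to name its baseline covariate, whereas a longitudinal model with PHQ-9 at weeks 0, 6 and 12 can carry baseline as a response. On that reading the follow-up-only benchmark describes an unlikely plan. If equal arm means are imposed, there is no gain to be had. **This stands as a limit on what can be claimed.** It does not remove the point. With free arm means there is still a loss, including when the triggered score is added, and the text does not rule that model out.

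The size is also uncertain. Neither r nor the baseline SD is in the documents, and at r = 0.3 the full package (always adjust, keep the trigger) moves relative variance only from 0.993 to 0.948. That is about 2% in standard error, or 0.07 points. **This stands.** The downside is also small: at r = 0 the cost is about 1% of variance.

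The 30% trigger rate follows from an assumed rule. Six to eight tests would give 26% to 34%, and gender will hardly vary in this population. **This stands too**: the simulation illustrates one possible reading of the SAP. The detectable differences do not depend on it.

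Finally, the propensity step may be needed if roll-out really was delayed. That is a reason to keep the step, not a reason to leave baseline PHQ-9 conditional.

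**Conclusion.** The concern holds. Neither document names a baseline PHQ-9 term in the primary model, and the SAP's only explicit use of baseline depression there is conditional. Always adjusting is at least as precise as the alternatives unless r is very low (below about 0.11 to 0.12 against follow-up only). At 43/42 and r = 0.5 with equal SDs, it lowers the detectable difference from 3.07 to 2.68 points against either follow-up only or change scores. Against follow-up only, the gain runs from 0.12 points (r = 0.3) to 0.87 (r = 0.7). Against change scores it runs from about 0.7 to 0.2 with equal SDs, and down to 0.01 with baseline SD 4 and r = 0.7.

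These figures rest on SD 5, no dropout, no clustering and assumed values of r. If the authors already intend a covariate or a common baseline mean, the gain is zero and only the wording needs to change. No bias under randomization and no error in the stated power is claimed.

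**What to change.** In the Effectiveness paragraph of both documents:

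- State that the primary GLMM always adjusts for baseline PHQ-9, as a covariate for the week 6 and week 12 scores. If patient-level randomization is confirmed, a week-0 response with equal arm means is an equivalent choice.
- Name the week-12 arm contrast as the treatment effect.
- Treat GAD-7 the same way, with its own baseline.
- Add this to the SAP's population comparison and propensity step. Drop that step only if patient-level randomization (Protocol, Objectives) is confirmed over the SAP's time-delay and delayed roll-out wording. Most of the gain remains if the step stays.
- Keep the care manager and clinic correlation terms and the optimization covariates.

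The cost is a short text edit and one or two degrees of freedom, about 0.01 to 0.02 PHQ-9 points in detectable difference. No new data are needed.

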Depressive and suicidality symptoms	PHQ-9 with BDI	TES: data gathered via IntelliCare and REDCap eTAU: data gathered routinely for COMPASS clinical care CMs or research team will enter these data in the study database.	Continuous
Anxiety symptoms	GAD-7	TES: data gathered via IntelliCare and REDCap eTAU: data gathered routinely for COMPASS clinical care CMs or research team will enter these data in the study database.	Continuous
Suicidal ideation	Columbia Suicide Risk Assessment	Data gathered routinely for COMPASS clinical care by Care Managers or research team and entered in the study database by the CM or research team	As needed
Demographics	Demographics Questionnaire	Participant self-report survey	0w
Health status	SF-36 (3 items)	Participant self-report survey	0w
Other mental health treatment	“Other Mental Health Treatment” Questionnaire*	Participant self-report survey	0w, 6w, 12w
Technology engagement, usability, usefulness, and satisfaction	TWEETS	Participant self-report survey	6w, 12w
Mobile phone competence	Mobile Phone Competence	Participant self-report survey	0w
Bond between patient and CMs	Working Alliance Inventory / Short Revised (WAI-SR); (BOND ONLY)	Participant self-report survey, Care Manager data entry	6w, 12w
Supportiveness of CMs	Supportive Accountability Inventory	Participant self-report survey	6w, 12w
Satisfaction with services	SIMH	Participant self-report survey	6w, 12w
Coaching user feedback	Coaching user feedback survey	TES only: Participant self-report survey	6w
	Coaching user feedback interview	TES only: Optional participant telephone interview	6w
Usability Interview	Usability Interview	TES only: Optional participant telephone interview	2w, 4w, 6w
Alcohol and Substance Use	Substance use information in the EMR	Medical records	Continuous
Comorbidities	Diagnoses from the EMR	Medical records	Continuous
Obstetrics information	Actual delivery date, complications in pregnancy, gestational age at delivery	Medical records	Continuous

STU#:00211815

Adherence	App/website usage, communication with CM	TES: app usage and text message data gathered by IntelliCare and transferred to the study team eTAU: website usage data gathered via website analytics tools	Continuous

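### The SAP carries no antenatal/postpartum term, although the protocol commits to moderation by that stratum and to within-stratum results; neither document says when stratum is assigned

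*Protocol*

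**What the plan says.** **Protocol (version 10.18.2023).** The Data Analysis Plan section commits to the stratum analysis directly: "We will examine moderation of treatment arm by strata (postpartum or antenatal), and present results within each strata". Its Power paragraph sizes that analysis: "we provide an estimate of effect that we can detect with 100 randomized participants, as well as within strata of 80 and 20". It reports "effect sizes of 1.41 and 0.65 in antenatal and postpartum populations, which correspond to differences of 7.03 and 3.26 on the PHQ-9", beside a whole-cohort figure: "We have 80% power to detect an effect size of 0.58 for the entire cohort".

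The Inclusion and Exclusion Criteria admit patients at any stage of pregnancy or up to three months after delivery. Assessments are at baseline, 6 and 12 weeks. Table 1 collects from medical records "Actual delivery date, complications in pregnancy, gestational age at delivery", but no analysis is said to use the delivery date.

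**SAP (04.15.24).** The moderation paragraph begins "We will examine any moderation of the effect of treatment arm on depressive symptoms by race, ethnicity, age, health status, substance/alcohol use, mobile phone" and goes on to phone competence and other mental health treatment. It closely matches the protocol's own moderator paragraph, but the separate stratum sentence in the protocol has no counterpart. The effectiveness paragraph compares the arms on demographics, health status, phone competence, baseline depression and other treatment, and brings in propensity adjustment if they differ. The power paragraph gives one whole-group figure, for 30 eTAU and 45 TES participants. The words antenatal and postpartum do not appear.

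**The concern.** Two plans for the same trial disagree on whether its main clinical subgroup is analysed. If the SAP governs, three things are lost:

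- the interaction and within-stratum results that the protocol commits to;
- adjustment of the primary model for a baseline factor that may well relate to the course of depressive symptoms;
- any check for imbalance on that factor, since it is not among the variables that can trigger propensity adjustment.

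The documents do not say whether allocation was stratified by perinatal status, so balance on it cannot be presumed.

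If the protocol governs instead, its strata lack a time of assignment. Someone enrolled in late pregnancy is antenatal at baseline and postpartum by week 12. Without a rule, that person could be classified either way, and the choice could be made after outcomes are seen.

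**Working it through.** **1. Was the stratum analysis really sized in the protocol?** Inputs from its Power paragraph: 80% power, SD 5, totals of 100, 80 and 20, with effect sizes "based on an independent t-test". Alpha, sidedness, allocation and attrition are not stated; I assume two-sided 5% and 1:1. For n per arm, solve for the d at which a t-test with 2n − 2 degrees of freedom and noncentrality d × √(n/2) has 80% power; points = 5 × d.

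| Group | Per arm, no loss | d (points) | Per arm, about 5% loss | d (points) | Protocol |
|---|---|---|---|---|---|
| 100 | 50 | 0.566 (2.83) | 47 and 48 | 0.581 (2.9) | 0.58 (2.9) |
| 80 | 40 | 0.634 (3.17) | 38 | 0.651 (3.26) | 0.65 (3.26) |
| 20 | 10 | 1.325 (6.62) | 9 | 1.407 (7.03) | 1.41 (7.03) |

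With about 5% loss (95, 76, and 19 rounded down to 9 per arm) all three figures reproduce, so the strata were deliberately sized. The loss itself is my inference. The text lists the strata as 80 then 20 but the effects as antenatal then postpartum. The larger detectable effect must belong to the smaller group, so antenatal is the stratum of 20 if the effects are labelled correctly.

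**2. Side by side.**

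| Element | Protocol | SAP |
|---|---|---|
| Arm-by-stratum moderation | Yes | Not mentioned |
| Within-stratum results | Yes | Not mentioned |
| Stratum in baseline comparison | No such comparison | Not listed |
| Detectable effect by stratum | 1.41 and 0.65 | None; one figure, 0.76 |
| When stratum is assigned | Not stated | Not stated |

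**3. What could a restored analysis show?** By normal approximation, the detectable interaction at 80% power is (1.96 + 0.84) × √(sum of 1/n over the four cells).

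- Strata of 20 and 80, 1:1: 2.80 × √(2/10 + 2/40) = 2.80 × 0.500 = 1.40 SD, or 7.0 PHQ-9 points.
- The protocol's current total is 85. At the same mix (an assumption) the strata are 17 and 68: 2.80 × √(2/8.5 + 2/34) = 2.80 × 0.542 = 1.52 SD, or 7.6 points.
- Within strata of 17 and 68, the t-test method gives 1.46 SD (7.3 points) and 0.69 SD (3.45 points).

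The first figure is about 2.4 times the whole-cohort difference (7.0/2.9).

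**4. How many antenatal entrants deliver by week 12?** The documents give no distribution of gestational age at entry. Assuming uniform entry over the last w weeks of pregnancy, the share is 12/w.

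| w | Share | Of 17 |
|---|---|---|
| 40 | 30% | 5.1 |
| 28 | 43% | 7.3 |
| 20 | 60% | 10.2 |

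That is about 5 to 10 of an assumed 17. It shows that the definition matters; it does not predict the trial.

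**The case against.** **Silence is not a decision.** A reader might infer that the SAP deliberately removed the analysis. The documents do not support that. The SAP gives no reason and does not say that it replaces the protocol's plan. Its delayed roll-out and propensity wording does not fit patient-level randomisation, so carried-over text is plausible. This stands as a limit on what can be claimed; the conflict remains.

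**The commitment is narrow.** The Objectives phrase "TES) intervention to enhanced treatment as usual (eTAU) within antenatal and postpartum women" can be read as simply naming the population, and Aim 2 lists moderators without perinatal status. This is fair. The commitment rests on the Data Analysis Plan sentence and the stratum power figures, which are explicit enough.

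**Deliveries do not bias the comparison.** A reader might infer that births during follow-up invalidate the within-stratum result, or that the protocol imposes a fixed label wrongly. Neither is supported. The protocol does not say whether stratum is fixed or changes over time, and strata set by status at entry preserve the randomised comparison. What remains is an undefined assignment time and a matter of interpretation: week-12 scores in the antenatal group would come from both pregnant and delivered patients.

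**Little can be learned from so small a stratum.** This is correct for testing. It argues for calling the results descriptive and fixing the definition in advance, not for leaving the two plans in conflict.

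**Conclusion.** The point holds as a conflict between the two documents and a missing definition. Followed as written, the SAP would not yield the arm-by-stratum and within-stratum results that the protocol commits to, and would not adjust for perinatal status. The overall randomised comparison is not invalidated.

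The restored analysis would be descriptive: the interaction has 80% power only for about 1.4 SD at 20/80, or about 1.5 SD at 17/68. These figures assume two-sided 5%, 1:1 allocation, no loss and, at 85, the same stratum mix. Antenatal as the smaller stratum is inferred from the effect sizes. The 30% to 60% delivering by week 12 rests wholly on assumed entry windows and should not be read as a finding about this trial.

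**What to change.** Reconcile the SAP with the protocol's Data Analysis Plan before the primary analysis:

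- define stratum as antenatal or postpartum status at randomisation;
- include the stratum main effect in the primary GLMM and, if the baseline comparison is kept, add stratum to its list;
- restore the arm-by-stratum interaction and the within-stratum estimates with confidence intervals, labelled descriptive;
- describe the antenatal result as 'enrolled during pregnancy', and report by arm how many had delivered by weeks 6 and 12, from the delivery dates already collected.

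A supportive model with a delivered-by-assessment indicator is optional. That indicator is a post-randomisation term and would tell little in about 17 people.

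The cost is SAP wording and one or two degrees of freedom: one for the main effect in the primary model and one for the interaction in the moderation model. No new data are needed.

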Execution of Stepped Care	Each time the PHQ-9 score is documented, the CM or the research team will indicate whether the stepped care protocol was executed in response to PHQ-9 total score.	Data gathered routinely for COMPASS clinical care. CMs will enter these data in the study database when documenting PHQ-9 scores.	Continuous

Self-report surveys and Care Mzanager data entry forms have been uploaded to the eIRB+ system for review. Please see the data handling section for a description of the procedures that will be used to obtain data from self-report surveys, interviews, CM data entry, medical record data extraction, IntelliCare data, and COMPASS website usage data.

DATA AND SPECIMEN BANKING

Deidentified data will be stored indefinitely for secondary analyses.

STUDY TIMELINES

Enrollment Timeline

Recruitment for the clinical trial will occur outside the context of usual Care Manager (CM) activities and will be managed by the research team with support from the Care Managers (CM). All patients judged as meeting perinatal depression or anxiety criteria by the research team who are at least 18 years of age will be offered participation and will be screened verbally by the research team and/or Care Managers (CM). If participants screen eligible, they will be directed to a digital version of the consent form, as described on Pg. 12. The research team will record the results of all recruitment contacts. We expect to enroll 100 participants through March 2024.

Timeline of Participant Activities

Active participation will last 12 weeks for each study participant. Participants will use the study interventions during the 12-week period and complete assessments according to the schedule laid out in table 2 below:

Table 2. Participant Activities

Method	Week 0	Week 2	Week 4	Week 6 Mid-Treatment	Week 12 End of Treatment
Self-report Survey	x			x	x
Usability Interview (optional)*		x	x	x	
Coaching User Feedback Interview (optional)*				x	
App and Website Usage	Continuous, unobtrusive				
Communication with Care Manager	Continuous, unobtrusive				
Medical Record Data	Continuous, unobtrusive				

* Optional Usability/User-Feedback Interviews (2w, 4w, 6w)

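### The protocol plans to randomise 85 but computes power for 100, and the SAP's 3.8-point figure rests on a roll-out premise and cannot be verified

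*Protocol*

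**What the plan says.** **Number of participants.** The Study Summary table of the protocol gives a sample size of 85. Study Endpoints agrees and splits it by site: "A total of 85 people (75 from Northwestern and 10 from Women and Infants Hospital) will be randomized". Study Timelines gives another number: "We expect to enroll 100 participants through March 2024".

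**Protocol power (Data Analysis Plan, Power).** The calculation is for a third description of the cohort: "we provide an estimate of effect that we can detect with 100 randomized participants, as well as within strata of 80 and 20". The result is "We have 80% power to detect an effect size of 0.58 for the entire cohort", stated as 2.9 PHQ-9 points at SD 5. For the strata it gives "effect sizes of 1.41 and 0.65 in antenatal and postpartum populations, which correspond to differences of 7.03 and 3.26 on the PHQ-9". The method and time point are described thus: "we provide effect size estimates for 12 month PHQ-9 scores based on an independent t-test". Study Endpoints, however, says: "Depressive symptoms and other outcomes will be measured at baseline and at 6 and 12 weeks".

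**SAP power.** The SAP takes 30 eTAU and 45 TES participants as a deliberately cautious recruitment figure, refers to delayed roll-out trials, assumes an ICC of 0.01 within clinics, and states 80% power for an effect size of 0.76 (3.8 points at SD 5). The protocol's Objectives section says "Randomization will occur at the patient level".

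Neither document states alpha, sidedness or loss to follow-up for these calculations. The protocol gives no allocation ratio, and the SAP gives no number or size of clinics.

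**The concern.** The 85 and the 100 cannot be explained as randomised versus enrolled, because Study Endpoints and the power paragraph both speak of people randomised. If 85 is the plan, no detectable difference has been stated for it, and the 80% claim belongs to a larger trial.

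The SAP adds a second detectable difference, 3.8 points against 2.9, built for a different design. A reader interpreting a null or borderline result cannot tell which figure describes the trial. The stratum figures matter too, because the protocol commits to presenting results separately for antenatal and postpartum participants.

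**Working it through.** **Method.** Two-sample t-test. With d the effect size and arms n1 and n2, the noncentrality is d × √(n1·n2/(n1+n2)) on n1+n2−2 degrees of freedom, and power is the probability that the noncentral t exceeds the 97.5% point of the central t. Differences in points are 5 × d.

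**Inputs.** From the documents: SD 5, 80% power, d = 0.58, N = 100 or 85, strata 80 and 20 (protocol); 30 vs 45, ICC 0.01, d = 0.76 (SAP). Assumed because not stated: two-sided 5%, 1:1 allocation, and loss of 0% or 5%.

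**Step 1: reproduce the protocol's figures.**

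| Group | Stated points | 1:1, no loss | 5% loss, rounded down per arm |
|---|---|---|---|
| All 100 | 2.9 | 50/50: 2.83 | 47/47: 2.92 |
| Stratum of 80 | 3.26 | 40/40: 3.17 | 38/38: 3.26 |
| Stratum of 20 | 7.03 | 10/10: 6.62 | 9/9: 7.03 |

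One 5% loss allowance matches all three printed values. It is nowhere stated, so it is an inference.

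**Step 2: move from 100 to 85, keeping the basis the same.**

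| Basis | Power for 2.9 points at 100 | Power at 85 | Points detectable with 80% power at 85 |
|---|---|---|---|
| No loss, 1:1 | 50/50: 81.9% | 42/43: 75.3% | 3.07 |
| About 5% loss, 1:1 | 47/48: 79.9% | 40/41: 73.2%; 39/40: 72.1% | 3.15; 3.19 |
| No loss, 2:3 (the SAP's ratio) | 40/60: 80.3% | 34/51: 73.5% | 3.14 |

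For example, at 42/43 the noncentrality is 0.58 × √(42×43/85) = 0.58 × 4.609 = 2.67 on 83 degrees of freedom.

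**Step 3: strata at 85.** No split is stated for 85. Carrying the 80:20 mix over gives 68 and 17, for illustration only. Before loss, 34/34 gives 3.45 points and 8/9 gives 7.28. With 5% loss rounded down, 32/32 gives 3.56 and 8/8 gives 7.53.

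**Step 4: the SAP's 3.8 points.** Without clustering, 30 vs 45 gives d = 0.669, or 3.35 points. With clustering, the design effect is 1 + (m−1) × 0.01 for m participants per clinic, and d is multiplied by its square root:

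- m = 10: 0.669 × √1.09 = 0.70, about 3.5 points
- m = 25: 0.669 × √1.24 = 0.745, about 3.7 points
- m = 28: 0.669 × √1.27 = 0.754, about 3.8 points
- m = 30: 0.669 × √1.29 = 0.760, 3.80 points
- m = 75: 0.669 × √1.74 = 0.88, about 4.4 points

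Unstated loss with no clustering also comes close: 24 vs 35 gives 3.78. For 85 individually randomised patients, power at d = 0.76 is 93% (42/43), or 92% with 5% loss (40/41), so 3.8 is not that trial's 80%-power difference.

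**The case against.** **The t-test is not the planned analysis.** The protocol says it used a t-test because the correlations over time were speculative; the analysis itself is a mixed model over baseline, 6 and 12 weeks. A reader might infer from Step 2 that the planned analysis is underpowered. The documents do not support that. As an illustration, adjusting for baseline scales the SD by √(1−r²). A baseline-outcome correlation r of about 0.33 would restore 80% power for 2.9 points at 85 with no loss, because (0.58/0.615)² = 0.89 = 1 − r². With 5% loss, r would need to be about 0.39 to 0.42. No correlation is given, so neither adequacy nor a shortfall can be shown for the mixed model. What stands is that the protocol's stated power, on its own method, does not apply to 85.

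**The SAP's figure may be right on its own terms.** A reader might infer that 3.8 is a miscalculation. That is not shown: about 28 to 30 per clinic gives it, and the missing clinic size makes it unverifiable rather than wrong. Nor is 30 + 45 = 75 a rival target, since the SAP calls it conservative and expects to exceed it.

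**The stratum figures may look like arithmetic errors.** They are not; they are consistent with a single undisclosed loss assumption.

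**It is a pilot and the shift is small.** Both are true, and they limit how much weight the point carries. But the sponsor chose to state 80% power, and the 12-month reference, evidently a slip, sits in the same paragraph.

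**Conclusion.** The point holds as an inconsistency to correct. At 85, the protocol's t-test has 75% power for 2.9 points with no loss (82% at 100), or 72-73% with about 5% loss (80% at 100). The detectable difference moves from 2.9 to about 3.1 points, or 3.15 to 3.2 with 5% loss. If 100 is the real plan, 2.9 stands. These figures rest on an assumed two-sided 5% test, SD 5 and 1:1 allocation; the SAP's 2:3 ratio changes them little.

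The SAP's 3.8 points belongs to a roll-out design that the protocol does not describe, and it cannot be verified from what the SAP states. Correcting these figures changes no test or decision rule. The SAP's propensity adjustment for time delay is a separate matter and is not judged here.

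**What to change.** 1. Choose 85 or 100 and use it in the protocol's Study Summary, Study Endpoints, Study Timelines and Power text, and in the SAP.
2. State one detectable difference for that number under patient-level randomisation in both documents, with alpha, sidedness, allocation, loss and SD. If 85: about 3.1 points before loss, or 3.15 to 3.2 with 5% loss. If 100: 2.9 can stay, with the loss assumption disclosed.
3. Recompute the antenatal and postpartum figures for the split actually expected, on the same loss assumption.
4. Replace the SAP's roll-out calculation. Keep an ICC term only if clustering by care manager or clinic is justified under patient-level randomisation, and then give the cluster size and design effect.
5. Change the 12-month reference to the 12-week end-of-treatment assessment.

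Suggested sentence: *With N = [number randomised], allocated [ratio], [x]% loss by week 12 and SD 5, a two-sided 5% t-test on 12-week PHQ-9 scores has 80% power for a difference of [y] points.*

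The cost is a short recalculation and wording in two documents, with no extra patients or data. If the number is 85, the stated figure becomes slightly less favourable.
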